12.1.4.3 Evaluation of Best Overall Response

The best overall response is the best response recorded from the start of the treatment until disease progression/recurrence (taking as reference for progressive disease the smallest measurements recorded since the treatment started). The patient's best response assignment will depend on the achievement of both measurement and confirmation criteria.

For Patients with Measurable Disease (i.e., Target Disease)

Target	Non-Target	New	Overall	Best Overall Response when
Lesions	Lesions	Lesions	Response	Confirmation is Required*
CR	CR	No	CR	≥4 wks. Confirmation**
CR	Non-CR/Non-	No	PR	
	PD			1 xxlxa Confirmation**
CR	Not evaluated	No	PR	≥4 wks. Confirmation**
PR	Non-CR/Non-	No	PR	

	PD/not evaluated			
SD	Non-CR/Non- PD/not evaluated	No	SD	Documented at least once ≥4 wks. from baseline**
PD	Any	Yes or No	PD	
Any	PD***	Yes or No	PD	no prior SD, PR or CR
Any	Any	Yes	PD	

^{*} See RECIST 1.1 manuscript for further details on what is evidence of a new lesion.

Note: Patients with a global deterioration of health status requiring discontinuation of treatment without objective evidence of disease progression at that time should be reported as "symptomatic deterioration." Every effort should be made to document the objective progression even after discontinuation of treatment.

For Patients with Non-Measurable Disease (i.e., Non-Target Disease)

Non-Target Lesions	New Lesions	Overall Response
CR	No	CR
Non-CR/non-PD	No	Non-CR/non-PD*
Not all evaluated	No	not evaluated
Unequivocal PD	Yes or No	PD
Any	Yes	PD

^{* &#}x27;Non-CR/non-PD' is preferred over 'stable disease' for non-target disease since SD is increasingly used as an endpoint for assessment of efficacy in some trials so to assign this category when no lesions can be measured is not advised

12.1.5 Duration of Response

Duration of overall response: The duration of overall response is measured from the time measurement criteria are met for CR or PR (whichever is first recorded) until the first date that recurrent or progressive disease is objectively documented (taking as reference for progressive disease the smallest measurements recorded since the treatment started).

The duration of overall CR is measured from the time measurement criteria are first met for CR until the first date that progressive disease is objectively documented.

Duration of stable disease: Stable disease is measured from the start of the treatment until the criteria for progression are met, taking as reference the smallest measurements recorded since the treatment started, including the baseline measurements.

^{**} Only for non-randomized trials with response as primary endpoint.

^{***} In exceptional circumstances, unequivocal progression in non-target lesions may be accepted as disease progression.

Version Date: 04-05-2021 v6.0

12.1.6 Progression-Free Survival

PFS is defined as the duration of time from start of treatment to time of progression or death or last follow-up, whichever occurs first.

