5. TREATMENT PLAN

5.1 Agent Administration

Once the investigator has signed the eligibility checklist, randomization may proceed. Patients meeting study entry criteria will be randomized to treatment ARM A or Arm B by the study statistician, [name]. Eligible subjects (eligibility confirmed and checklist signed) will be assigned to a treatment arm until 44 subjects (22 in each arm) have been enrolled. The study coordinator will update Oncore and ERMS reflect randomization information.

Following randomization, patients should begin protocol treatment within 5 business days. Issues that would cause treatment delays should be discussed with the Principal Investigator.

Treatment will be administered on an *outpatient* basis. Reported adverse events and potential risks are described in Section 7. Appropriate dose modifications are described in Section 6. No investigational or commercial agents or therapies other than those described below may be administered with the intent to treat the patient's malignancy.

Patients will be randomly assigned 1:1 using block randomization with a block of 6 patients. Randomization schema will be kept in the research pharmacy.

Patients with unresectable stage III or stage IV melanoma being treated with FDA approved standard of care immune checkpoint combination therapy with Ipilimumab and Nivolumab are eligible for this trial.

Patients will be randomized 1:1 to either continue therapy with standard of care Ipilimumab and Nivolumab (ARM A) or standard of care Ipilimumab and Nivolumab plus **4 doses of weekly Rituxan** (ARM B).

Patients enrolling on this study following treatment failure on single agent anti-PD-1 will be distributed equally between arms A and B of the study.

Induction Phase:

ARM A: Cycles 1-4

Each cycle is 21 days and includes Ipilimumab (3 mg/kg) on day 1 plus Nivolumab (1 mg/kg) on Day 1.

ARM B. Cycles 1-4

Each cycle is 21 days and includes Ipilimumab (3 mg/kg) on day 1 plus Nivolumab (1 mg/kg) on

Version Date: 04-05-2021 v6.0

Day 1. In addition, patients will receive 4 weekly doses of Rituxan (first dose 375 mg/m2 IV and then 3 weekly doses of 1400 mg Rituxan Hycela subcutaneous, as per current label for Rituxan Hycela).

First dose of Rituxan will be administered 1 week after start of Ipi/Nivolumab therapy. 3rd dose of Rituxan will be administered on day 2 of cycle 2 after infusion of Ipi/Nivo on week4.

Continuation Phase:

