5.3 Duration of Follow Up

Patients will be followed for 4 weeks after removal from study or until death, whichever occurs first. Patients removed from study for unacceptable adverse event(s) will be followed until resolution or stabilization of the adverse event.

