5.4 Criteria for Removal from Study

Patients will be removed from study when any of the criteria listed in Section 5.2 applies. The reason for study removal and the date the patient was removed must be documented in the Case Report Form.

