11. STUDY CALENDAR

Schedules shown in the Study Calendar below are provided as an example and should be modified as appropriate.

Baseline evaluations are to be conducted within 3 weeks prior to start of protocol therapy. Scans and x-rays must be done \leq 4 weeks prior to the start of therapy. In the event that the patient's condition is deteriorating, laboratory evaluations should be repeated within 48 hours prior to initiation of the next cycle of therapy.

All protocol visits have a plus or minus 3 business day window.

Rituxan should be given after ipi/nivo infusion for subjects on Arm B. The timing of Rituxan is 1-2 days (preferably 1 day) following ipi-nivo infusion.

		1	ı	ı						1	1					
	Pre- Study	Wk 1	Wk 2	Wk 3	Wk 4	Wk 5	Wk	Wk	Wk 8	Wk 9	Wk 10	WK 12	Wk 13	WK 17	WK 21	Off Study
IPI 3mg/kg + Nivo 1mg/kg		X			X			X			X					
Nivo 480mg IV ^a													X	X	X	
Rituxan IV (loading dose)			X													
Rituxan SQ				X	X	X										
Informed consent	X															
Demographics	X															
Medical history	X															
Con Medications	X	X	X	X	X			X			X		X	X	X	X
Physical exam	X	X			X			X			X		X	X	X	X
Vital signs	X	X	X	X	X			X			X		X	X	X	X
Height	X															
Weight	X	X	X	X	X			X			X		X	X	X	X
Performance status	X	X			X			X			X		X			X
CBC w/diff, plts	X	X	X	X	X			X			X		X	X	X	X
Serum chemistry with LDH	X	X	X	X	X			X			X		X	X	X	X
EKG (12-lead)	X															
Adverse Event	X	X	X	X	X			X			X		X	X	X	X
Radiologic Evaluation ^b	X											X				
B-HCG	X															
Hepatitis B (HepB surface antigen and HepB core antibody), Hep C and HIV serology	X															
TSH, Free T, ACTH, cortisol	X				X			X			X		X	X	X	X
Blood correlative	X		X		X						X		X			X
Fresh Tissue Biopsy ^c	X				X											

^a given every 4 weeks starting at Week 13 for up to 13 doses.

^b CT scans n/c/a/p with contrast every 12 weeks for the first two years, then every 6 months for five years. MRI brain with contrast should be done at baseline, then every 6 months for patients with no history of CNS mets as per standard of care; every 3 months for those with a history of CNS metastases for two years, then every 6 months. CT head can be used for patients with a contraindication to MRI.

^C Tissue biopsy before week 4 is optional but encouraged whenever possible.

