14. STATISTICAL CONSIDERATIONS

14.1 Study Design/Endpoints

Endpoints:

Primary:

• Primary endpoint is the rate of CTC (v5.0) grade 3 or greater immune-related adverse events at 6 months of follow up.

Secondary:

- Rate of CTC (v5.0) toxicity related to Rituxan.
- Objective tumor response as assessed by RECIST v1.1 and irRECIST at 12 weeks and every 12 weeks thereafter.
- Rates of overall and progression-free survival at 1 year following initiation of therapy.

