14.2 Sample Size/Accrual Rate

This is an open-label, 2-arm phase II clinical trial to study the differential effect in the risk of IRAEs between treatment and control groups. A sample size of 22 patients per arm (44 total) will provide us approximately 80% power to detect a 40% difference in the rates of developing ≥grade 3 IRAE within 6 months follow up between the control and the treatment arm (estimated to be 60% in the control arm, Callahan et al; J Clin Oncol. 2017 Dec 1;35(34):3815-3822). The sample size calculation is based on Fisher's exact test at a one sided significance level of 0.05 under the following assumptions: 1). Patients will be randomized in 1:1 ratio of the treatment to control arm. 2). Approximately 60% patients in the placebo arm will develop > grade 3 IRAE

within 6 months based on our pilot study. 3). The treatment will reduce the rate of ≥ grade 3 IRAE to 20% in the treatment arm. In a recent study, the rate of objective response following combination checkpoint blockade was 42% (Callahan et al; J Clin Oncol. 2017 Dec 1;35(34):3815-3822). In order to monitor potentially adverse impact of Rituxan on checkpoint blockade, we will utilize early stopping rules based on an adaptive design wherein trial will be stopped if we have strong evidence of rates of objective response of <30%. The trial will be stopped early in the unlikely event that less than 2 patients among the first 12 patients treated by Rituxan respond to therapy. If the rate of objective response is > 30%, the probability that at least two out of first twelve patients will achieve an objective response of at least a PR for the first 12 patients is approximately 92%. Hazard ratios and corresponding two-sided 95% confidence intervals will be estimated using Cox-proportional hazards model, with the treatment group as a single covariate. Progression-free and overall survival curves, median with 95% confidence intervals, and progression-free survival rates at 6 months will be estimated with the use of Kaplan-Meier method. Biostatistics support for the study will be provided by biostatistics core resource of Winship Cancer Center.

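### PFS is followed to last follow-up rather than to the last tumour assessment, so contact time without an assessment counts as progression-free

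*Combined protocol and SAP*

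**What the plan says.** Section 12.1.6 gives the only definition: "PFS is defined as the duration of time from start of treatment to time of progression or death or last follow-up, whichever occurs first". It does not call last follow-up a censoring date and does not link it to imaging.

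Section 14.1 lists as a secondary endpoint "Rates of overall and progression-free survival at 1 year following initiation of therapy". Section 14.2 names the methods: "Hazard ratios and corresponding two-sided 95% confidence intervals will be estimated using Cox-proportional hazards model", and "progression-free survival rates at 6 months will be estimated with the use of Kaplan-Meier method". It gives no censoring rule, and neither does any other section.

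On assessments, footnote b of the Section 11 calendar sets "CT scans n/c/a/p with contrast every 12 weeks for the first two years", without reference to arm or treatment status. The calendar's Off Study column marks examination, laboratory tests and adverse events, but not radiology.

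On leaving the study, Section 5.4 states "Patients will be removed from study when any of the criteria listed in Section 5.2 applies", and the Section 5.2 criteria include unacceptable adverse events. Section 5.3 gives a general follow-up of 4 weeks after removal and adds "Patients removed from study for unacceptable adverse event(s) will be followed until resolution or stabilization of the adverse event". It does not mention scans.

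**The concern.** Progression is found mainly at scheduled assessments. A patient who is no longer assessed but is still seen cannot have most progressions recorded, yet under Section 12.1.6 stays in the risk set as progression-free until the last contact. Kaplan-Meier and Cox both treat that time as observed, so the curve is pulled upward.

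Three features of the plan can produce such contact: follow-up of an adverse event until it settles, off-study visits with no imaging marked, and the vital-status information needed for 1-year overall survival.

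The stake is the safety of the strategy for tumour control. Section 2.4 says that approaches aimed at immune-related events are viable only if tumour immunity and the durability of regressions are preserved. PFS informs that judgement, and unassessed time that differs between arms would distort it.

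**Working it through.** **Plan's own figures.** No figure is stated for PFS. The one powered comparison (22 per arm, 60% against 20%, one-sided Fisher exact test at 0.05) reproduces at 0.791 against the stated 80% or so. It does not bear on the PFS rule.

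**Inputs from the document.** Scans every 12 weeks (Section 11); Grade 3+ immune-related event rates of 60% and 20%, and 22 patients per arm (Section 14.2).

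**Assumptions, not in the document.** Exponential PFS with median 52 weeks and no true difference between arms; one third to one half of patients with such an event have no scan after week 12 but are seen for a further 4, 13, 26 or 41 weeks; leaving is unrelated to progression; death after progression has a median of 39 weeks.

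**How many patients.** Events expected: 22 × 0.60 = 13.2 in Arm A and 22 × 0.20 = 4.4 in Arm B. If one third leave scanning: 13.2/3 = 4.4 against 4.4/3 = 1.5 patients.

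**Longest contact, by hand, ignoring deaths.** With scan-detected progression, the 1-year rate is the rate at the week-48 scan.
- S(12) = 0.5^(12/52) = 0.852
- S(48) = 0.5^(48/52) = 0.527
- A leaver seen to week 53 is held at S(12) instead of falling to S(48), an excess of 0.852 − 0.527 = 0.325.
- Leavers as a share of each arm: A, 0.60 × 1/3 = 0.20 to 0.60 × 1/2 = 0.30; B, 0.20 × 1/3 = 0.067 to 0.20 × 1/2 = 0.10.
- Overstatement in Arm A: 0.20 × 0.325 = 6.5 points to 0.30 × 0.325 = 9.8 points.
- False gap, A minus B: (0.20 − 0.067) × 0.325 = 4.3 points to (0.30 − 0.10) × 0.325 = 6.5 points.

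**Allowing for deaths.** PFS counts death, and some unscanned progressors die while still in contact. Simulating with the post-progression death process reduces the gap:

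| Contact after the week-12 scan | Scans missed while in contact | False 1-year gap (A minus B) |
|---|---|---|
| 4 weeks (to week 16) | none | about nil |
| 13 weeks (to week 25) | week 24 | 1-1.5 points |
| 26 weeks (to week 38) | weeks 24, 36 | 2-3 points |
| 41 weeks (to week 53) | weeks 24, 36, 48 | 3-4 points |

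**Wider assumptions.** With median PFS of 26 or 52 weeks, one third to all of these patients leaving at a time uniform over 26 weeks, and post-progression death at 2.5 times the PFS median, the gap is 0.3-2.7 points with 4 weeks of contact, 2.6-12.3 with 26 weeks and 4.4-16.4 with 78 weeks. Censoring every leaver at the last scan left at most 0.7 points, which is simulation noise.

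**Against the precision available.** With PFS near 53% and 22 per arm, ignoring censoring, the 95% half-width for the 1-year difference is 1.96 × √(2 × 0.53 × 0.47/22) = 0.295, about ±30 points.

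**Testing the remedy.** Under the 39-week death assumption, censoring survivors at the last scan while counting every later death reverses the gap by up to about 1-2 points, because deaths among leavers are kept while their event-free time is dropped. Also censoring deaths that follow two or more missed scans leaves under 1 point.

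**The case against.** The bias needs patients who stop being assessed but stay in contact, and the document does not say that this happens. Footnote b of Section 11 keeps scans going for two years regardless of treatment. A note in Section 12.1.4.3, written for symptomatic deterioration, asks that progression still be documented after treatment stops. Section 2.3 reports discontinuation of therapy in up to a third of patients, which is not discontinuation of scanning. The general follow-up after removal is 4 weeks, where the main calculation gives no bias. Since Section 5.2 restricts protocol-specific therapy to rituximab, stopping ipilimumab and nivolumab for toxicity is not clearly removal from study. Contact is not blind to progression either: Section 12.1.3 accepts caliper measurement of superficial lesions, and Section 12.1.4.2 gives weight to the treating physician's opinion on non-target lesions. Last follow-up is undefined and may have been meant as the last assessment.

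Most of this stands and limits the size of the problem. It does not supply the missing rule. Neither the calendar nor the note says how to censor a patient who was not scanned, and Section 5.3 sets no time limit on adverse-event follow-up. If scanning proves complete, the corrected wording changes almost nothing.

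Two stronger readings are tempting. A reader might infer that Arm A will be favoured and Rituxan made to look harmful. That needs the untested 60% against 20% hypothesis to be true and equal loss of scanning per event. With equal exit rates the gap vanishes, though both curves stay too high; exits for Rituxan toxicity could offset or reverse it. A reader might also infer that starting the clock at treatment breaches the intent-to-treat commitment in Section 6. That phrase concerns patients who stop Rituxan for toxicity, who have already started treatment.

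**Conclusion.** The definition should be corrected. As written, time after the last tumour assessment counts as progression-free, the plan leaves room for such time, and the effect is to overstate PFS.

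A difference between arms is conditional, not established. Under the main assumptions it runs from about nil to 3-4 points at 1 year, depending on how long unscanned patients remain in contact. The wider ranges require more patients to leave scanning or longer contact, and the document supplies neither figure. All these ranges also assume that leaving is unrelated to progression. The effect is small beside ±30 points, and PFS is a secondary endpoint with no power claim. The case for change rests on a clear defect with a cheap remedy.

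The time origin is a minor matter. Section 5.1 says "Following randomization, patients should begin protocol treatment within 5 business days", and Section 14.1 uses the same treatment-start origin. Only a patient randomised and never treated would lack a PFS time.

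**What to change.** Replace the definition in Section 12.1.6 with wording to this effect:

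- PFS is the time to first progression by RECIST 1.1 or death from any cause.
- Patients alive without documented progression are censored at their last adequate tumour assessment, or at the time origin if they have none. Define adequate to include the clinical measurements that Section 12.1.3 accepts.
- If progression or death follows two or more consecutive missed assessments, the patient is censored at the last adequate assessment before the gap.
- A sensitivity analysis counts those later progressions and deaths as events.
- Completeness of scheduled scans is reported by arm.

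Sections 5.3 and 11 should also be reconciled so that it is clear whether the scan schedule applies after removal from study. Starting the clock at randomisation, with the same origin for the 1-year rates in Section 14.1, is an optional alignment.

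The cost is a few sentences and one extra analysis, using assessment, death and randomisation dates that the trial should already hold. The downside is slightly less follow-up counted and somewhat wider intervals.

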Winship Protocol #: 4457-18; Version 6.0 04 05 2021

TITLE: A Randomized Phase 2 Study of Rituxan Hycela in patients with advanced melanoma undergoing combination immune checkpoint blockade with nivolumab and ipilimumab.

*Principal Investigator: [name].

[name]

[name] [contact] (phone) [contact] (fax)

[contact]

Co-Investigators: [name].

[name] [contact](phone) [contact] (fax) [contact]

[name].

[name], M.D.

[name]. [name]. [name]

Statistician:

[name] Ph.D Winship Cancer Institute of Emory University [name] Tel (O): [contact] [contact]

[figure not shown]
Study Coordinator:

[name] [name] [contact] (phone) [contact] (fax) [contact]

Supplied Agent: Rituximab (supplied by Genentech, South San Francisco, CA)

IND: Exempt

SCHEMA

Trial Design. All patients have chosen ipi/nivo as standard of care (SOC) treatment. They will be randomized prior to the first dose of ipi/nivo to receive either ARM A: SOC Ipilimumab + Nivolumab only with no additional therapy or ARM B: Standard of care Ipilimumab and Nivolumab, + 4 weekly doses of Rituxan (first dose of IV Rituxan followed by 3 weekly doses of subcutaneous Rituximab hycela) beginning 1-2 days following the first dose of Ipilimumab and Nivolumab. SOC Ipi/Nivo is ipilimumab 3mg/kg every 3 weeks for 4 doses and nivolumab 1mg/kg every 3 weeks for 4 doses followed by nivolumab 480 mg IV every 4 weeks x 12 doses or until disease progression or intolerant adverse event.

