5.2 Duration of Therapy

The protocol-specific therapy in this study is restricted to only 4 weekly doses of rituximab in patients randomized to the Rituximab-arm.

In the absence of treatment delays due to adverse event(s), treatment may continue for 4 weekly doses of Rituxaimab (or observation) or until one of the following criteria applies:

- Disease progression,
- Intercurrent illness that prevents further administration of treatment,
- Unacceptable adverse event(s),
- Patient decides to withdraw from the study, or
- General or specific changes in the patient's condition render the patient unacceptable for further treatment in the judgment of the investigator.

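### PFS and the 1-year survival rates are timed from start of treatment, so a patient randomized but never treated drops out of the between-arm comparison

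*Combined protocol and SAP*

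**What the plan says.** - **PFS (12.1.6):** "PFS is defined as the duration of time from start of treatment", ending at the earliest of progression, death and last follow-up.
- **1-year rates (14.1, secondary endpoints):** "Rates of overall and progression-free survival at 1 year following initiation of therapy". OS has no other definition.
- **Order of events (Schema):** "They will be randomized prior to the first dose of ipi/nivo".
- **Gap to first dose (5.1):** "Following randomization, patients should begin protocol treatment within 5 business days".
- **Analysis (14.2):** the trial is open-label, with 22 patients per arm. Hazard ratios come from a Cox model with treatment group as the only covariate, and survival curves from Kaplan-Meier.
- **Analysis set:** none is stated for PFS or OS. The only intent-to-treat wording, in section 6, covers patients who stop Rituxan because of toxicity. It does not cover patients who are randomized and never start.

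**The concern.** Randomization protects a comparison when every randomized patient is counted, in the arm assigned, from a point that the assignment cannot influence. Here the clock starts at a later event. A patient who withdraws or deteriorates between randomization and first dose never reaches that event.

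Assignment is open-label and Arm B carries four extra weekly Rituxan doses, so loss before first dose could differ by arm. Comparing 1-year OS and PFS is a listed secondary objective (1.2). Section 2.4 says that preventing IRAEs is clinically viable only if tumor control is not harmed. These endpoints are part of the evidence on that, and with 22 per arm one or two missing patients matter.

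**Working it through.** **1. The plan's own figure.** The only stated power is for the primary endpoint: 22 per arm, 60% against 20%, Fisher's exact test, one-sided 0.05, about 80% (14.2). Summing the product of the two binomial probabilities over all outcomes with one-sided Fisher p ≤ 0.05 gives 0.791, which reproduces it. No power or event count is stated for PFS or OS, so no stated figure depends on the survival time origin.

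**2. Can a non-starter be placed under the written rules?**

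| Question | Where | Answer |
|---|---|---|
| When is the patient randomized? | Schema | Before first ipilimumab/nivolumab |
| When does the PFS clock start? | 12.1.6 | Start of treatment |
| When does the 1-year clock start? | 14.1 | Initiation of therapy |
| Is there an all-randomized survival set? | 6, 12.1, 14 | Not stated |

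A non-starter has no start date, hence no survival time. Entering the patient as censored at time zero would be the same as exclusion, because such a patient contributes to no risk set.

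**3. How far could the 1-year rate move?** Inputs: n = 22 per arm (14.2); k = non-starters in the arm (assumed 1 to 3); r = 1-year rate among starters (assumed). The documents give neither k nor r. The all-randomized rate is lowest if every non-starter has an event by 1 year and highest if none does:

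- lower = r(22 − k)/22
- upper = [r(22 − k) + k]/22
- width = k/22

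For r = 50%:

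- k = 1: 10.5/22 = 47.7% to 11.5/22 = 52.3%
- k = 2: 10/22 = 45.5% to 12/22 = 54.5%
- k = 3: 9.5/22 = 43.2% to 12.5/22 = 56.8%

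With other assumed rates among starters:

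| k | r = 40% | r = 70% |
|---|---|---|
| 1 | 38.2–42.7% | 66.8–71.4% |
| 2 | 36.4–45.5% | 63.6–72.7% |
| 3 | 34.5–48.2% | 60.5–74.1% |

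**4. Scale.** At r = 50% the largest departure in either direction is k/44, which is 2.3, 4.5 or 6.8 points. The binomial standard error of a 50% rate in 22 patients is √(0.5 × 0.5/22) = 10.7 points. The possible shift is smaller than sampling error, but it would be systematic and would not appear in the confidence interval.

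**The case against.** The best case for leaving the plan alone is that non-starters should be rare. All patients have already chosen ipilimumab/nivolumab as standard care (Schema), the eligibility checklist is signed before randomization (4.2a, 5.1), and treatment should begin within 5 business days. The endpoints are secondary. This stands, and it limits the likely size; it does not supply a rule for a non-starter.

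A second objection also stands. Withdrawal means removal from study (5.2, 5.4), and 5.3 then gives only 4 weeks of follow-up, which ends before the first 12-week scan. Moving the origin alone would bring in early deaths, but most surviving non-starters would be censored within weeks and would barely change the 1-year estimate. The change needs a follow-up rule with it.

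Two stronger readings are tempting, and the documents do not support them.

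- **Arm B's clock starts later than Arm A's.** A reader might infer this from 5.2, "The protocol-specific therapy in this study is restricted to only 4 weekly doses of rituximab in patients randomized to the Rituximab-arm", together with 5.1, "First dose of Rituxan will be administered 1 week after start of Ipi/Nivolumab therapy". But 5.1 has patients in both arms begin protocol treatment within 5 business days of randomization. Arm A never receives Rituxan, and 5.1 itself puts Arm B's first Rituxan dose a week after ipilimumab/nivolumab. Section 12.1.1 dates toxicity evaluability from first ipilimumab/nivolumab, and 5.2 concerns how long Rituxan is given. A later origin would also shorten Arm B's times, so it would not hand that arm an event-free lead. Separately, the Schema has Rituxan "beginning 1-2 days following the first dose of Ipilimumab and Nivolumab", and the calendar text agrees with that, while 5.1 and the calendar grid place it a week after. Those passages must be reconciled, but this point does not depend on them.
- **Two patients move the rate by 10 points.** With two non-starters, 11/20 = 55% and 9/20 = 45% are two opposite assumed scenarios, each 5 points from 11/22 = 50%. The 10 points are the distance between the two, not the error in either.

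**Conclusion.** The point holds for the time origin and the missing analysis set. As written, PFS and the 1-year OS and PFS rates start at a post-randomization event, and a randomized patient who never starts cannot enter the comparison. If everyone starts, nobody is lost. With 1 to 3 non-starters in an arm and a 50% rate among starters, the all-randomized 1-year rate is uncertain by up to 2.3 to 6.8 points either way. Those counts and that rate are assumptions. No offset between arms is claimed, and the planned sample size, alpha and primary power are unaffected. This is a modest weakness in secondary endpoints, worth correcting because the correction is cheap.

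**What to change.** - **12.1.6 and 14.1:** define PFS and OS as time from the date of randomization, in all randomized patients in the arm assigned. Read the 1-year rates at 12 months from randomization.
- **Non-starters:** keep collecting survival and whatever progression status is available, with 5.3 amended to allow it. Otherwise censor at last known status.
- **Sensitivity analysis:** repeat PFS and OS from first ipilimumab/nivolumab among patients who started, naming that dose as the origin in both arms. Report the number of non-starters by arm.

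**Cost:** a few wording changes, a few pre-treatment days in each survival time, and a little follow-up of non-starters. Section 5.1 already has randomization information entered in the study systems.
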